3.4.3 Comparison with external control.....	25
3.5 MULTIPLICITY ISSUES	26
3.6 SAFETY ANALYSES	27
3.6.1 Extent of exposure	28
3.6.2 Adverse events	29

3.6.3	Additional safety assessments.....	32
3.6.3.1	Laboratory variables, vital signs and electrocardiograms (ECGs).....	32
3.6.3.2	Analysis of suicidality assessment.....	34
3.7	OTHER ANALYSES	34
3.7.1	Other variables and/or parameters	34
3.7.1.1	Pharmacokinetic (PK) analyses	34
3.7.1.2	Pharmacodynamic (PD) analyses.....	34
3.7.1.3	PK/PD analysis	35
3.8	INTERIM ANALYSES	35
3.9	CHANGES TO PROTOCOL-PLANNED ANALYSES.....	35
4	SAMPLE SIZE DETERMINATION	37
5	SUPPORTING DOCUMENTATION	38
5.1	APPENDIX 1 LIST OF ABBREVIATIONS	38
5.2	APPENDIX 2 PARTICIPANT DISPOSITIONS	38
5.3	APPENDIX 3 DEMOGRAPHICS AND BASELINE CHARACTERISTICS, PRIOR OR CONCOMITANT MEDICATIONS	40
5.4	APPENDIX 4 DATA HANDLING CONVENTIONS	42
6	REFERENCES.....	47

LIST OF TABLES

Table 1 - Objectives and endpoints.....	7
Table 2 - Summary of primary estimand for main endpoints	10
Table 3 - Populations for analyses	12
Table 4 - Sorting of AE tables	30
Table 5 - Analyses of adverse events	31
Table 6 - Selections for AESIs	32
Table 7 - Analyses window definition of efficacy variables	42
Table 8 - Analyses window definition of safety variables.....	43
Table 9 - Analyses window definition of PD variables.....	45

VERSION HISTORY

This amended statistical analysis plan (SAP) for study ACT16970 is based on the Amended Clinical Trial Protocol 05 dated 13-Dec-2023. The first participant was randomized on 28-Apr-2022. The initial SAP V1 was approved before the interim analysis for futility was conducted. This amended SAP is approved before the first database lock.

Major changes in statistical analysis plan

SAP Version	Approval Date	Changes from Protocol Amendment	Rationale
1	28-Apr-2023	
Disease duration (from first symptom onset to the screening visit) and the corresponding by-visit interaction are added as covariates in the Part A primary analysis model.
 
[REDACTED]. Instead, each of the 5 dimensions will be included in the analysis.
	Based on clinical input Index score is not really used for regulatory/clinical development purposes

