1 INTRODUCTION

1.1 STUDY DESIGN

This is a Phase 2, multicenter, randomized, double-blind, placebo-controlled, 2 parallel-group study to evaluate the efficacy and safety of SAR443820 in adult participants with amyotrophic lateral sclerosis, followed by an open-label extension.

Part A is a 24-week, double-blind, placebo-controlled part, preceded by a screening period of up to 4 weeks before Day 1. After a screening phase of up to 4 weeks, participants will be randomized in a ratio of 2:1 to receive 20 mg BID SAR443820 (n=174) or placebo BID (n=87). Randomization will be stratified by the geographic region of the study site (Asia, Europe or North America), region of ALS onset (bulbar or other areas), use of riluzole (yes or no), use of edaravone (yes or no), and use of the combination of sodium phenylbutyrate and taurursodiol (named Relyvrio in the USA and Albrioza in Canada) (yes or no). Participants will attend in-clinic study assessments at baseline (Day 1), Week 2, Week 4, Week 6, Week 8, Week 10, Week 12, Week 16, Week 20 and Week 24. All ongoing participants at Week 24 will rollover to open-label extension Part B. Participants who discontinue the treatment or choose not to enter Part B will have their follow up visit 2 weeks after the last dose of the study intervention.

Part B is an open-label, long-term extension of Part A, which starts from Week 24 and continues up to Week 106. The study intervention assignment of participants at randomization in Part A will remain blinded to Investigators, participants, and site personnel until the end of Part B unless there is medical need to unblind the study intervention assignment. All participants will receive 20 mg BID SAR443820 in Part B starting from Week 24, except those who discontinue IMP treatment permanently in Part A. Based on a data review, and in accordance with Data Monitoring Committee (DMC) recommendations, sites have been instructed on 5th December 2023 to pause the administration of SAR443820 in Part B (open-label extension) immediately. All participants in Part B will be encouraged to continue follow-up visits, but no doses of SAR443820 should be administered. Rollover to Part B for follow-up visits after completing Part A is also encouraged, but without taking SAR443820 in Part B. The decision of whether resuming SAR443820 administration in Part B will be made based on DMC recommendation when Part A data is available and benefit risk evaluation is made.

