The study duration includes an up to 4-week screening period, 24-week double-blind treatment period in Part A, 80-week open-label treatment period (Part B) and 2-week post-treatment follow-up period, with a maximum total study duration of 110 weeks.

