3 STATISTICAL ANALYSES

3.1 GENERAL CONSIDERATIONS

In general, continuous data will be summarized using the number of observations available, mean, standard deviation (SD), median, interquartile range (Q1, Q3), minimum, and maximum.

Categorical and ordinal data will be summarized using the count and percentage of participants.

Efficacy data will be analyzed in the ITT population, except CAFS endpoints in Part A and Part B will be analyzed in the mITT population. Safety data will be analyzed in the safety population, unless specified otherwise.

In Part A, baseline values are defined as follows. The baseline values of NFL, CHI3L1, the cytokine and chemokine panel in serum, sTREM2 in plasma and $p75^{ECD}$ in urine, are defined as the average value from samples collected at the screening visit and at Day 1 prior to the first dose of the study intervention. For the C-SSRS, the baseline value will be the worst assessment between the past 6 months evaluation at screening and the since last visit evaluation on Day 1. For the other efficacy and safety assessments, the baseline values are defined as the last available value prior to the first dose of study intervention. For participants randomized but not treated, the baseline value is defined as the last available value before randomization. Unless otherwise indicated, 2-sided p-values and 95% confidence intervals [CI(s)] will be provided for efficacy assessment of treatment differences. Unless otherwise specified, analyses will be performed by treatment group (and overall for baseline and demographics characteristics).

Efficacy analyses in Part B will be conducted accumulatively according to the treatment group allocated by randomization in Part A (ie, Placebo/SAR443820 versus SAR443820/SAR443820). Baseline values defined above for Part A will be used as the baseline in the efficacy analyses for Part B, unless otherwise noted. Safety analyses in Part B are stated in [Section 3.6](#).

Observation period

The observation period for safety will be divided into 4 segments:

- The **pre-treatment period** is defined as the period up to first investigational medicinal product (IMP) administration.
- The **on-treatment period** (ie, treatment-emergent (TE) period) **for the Part A** is defined as the period from the first IMP administration to the earliest of 1) last IMP administration + 14 days, 2) first IMP in Part B, 3) death date, or 4) last contact date.

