3.3 SECONDARY ENDPOINT(S) ANALYSIS

The secondary endpoints detailed in this section are as follows:

Part A

- CAFS at Week 24
- change from baseline in SVC to Week 24
- change from baseline in muscle strength to Week 24
 - change from baseline in megascore to Week 24
 - change from baseline in grip strength to Week 24

- change from baseline in ALSAQ-5 to Week 24
- change from baseline in serum NfL to Week 24

Part B

- CAFS at Week 76 and Week 104
- change from baseline in the ALSFRS-R total score to Week 52, Week 76, and Week 104
- time from baseline to occurrence of either death or permanent assisted ventilation (>22 hours daily for >7 consecutive days), whichever comes first
- time from baseline to the occurrence of death
- change from baseline in SVC to Week 52, Week 76, and Week 104
- change from baseline in ALSAQ-5 to Week 52, Week 76, and Week 104
- change from baseline in serum NfL to Week 52

Other secondary endpoints analyses are defined in [Section 3.6.2](#) (AE, SAE), [Section 3.6.3.1](#) (laboratory abnormalities), [Section 3.7.1.1](#) (PK) and [Section 3.7.1.2](#) (PD).

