3.4.3 Comparison with external control

A matched analysis using data from historical clinical trial database (for example, PROACT) as a control will be conducted to demonstrate the superiority of SAR443820 on slowing down disease progression and prolonging survival over 104 weeks of treatment period.

Matching procedure

1. Pre-matching filtering: The participants in the historical clinical trial database will be filtered by the following factors that match our trial eligibility criteria and duration:
 - Age 18 – 80 years, inclusive
 - First ALS symptom onset ≤ 2 years
 - Baseline SVC (%) $\geq 60\%$
 - Baseline ALSFRS-R decline rate $\geq 0.5/\text{month}$
2. Propensity score matching: Propensity score matching seeks to balance the distributions of known prognostic covariates in treatment and control group to resemble what would occur had the treatment been randomly assigned. A logistic regression for the treatment group as the dependent variable is performed to obtain the propensity score with the abovementioned matching variables, using all the participants (planned for 174) randomized to the SAR443820 arm and the participants from the historical clinical trial database after filtering as described above. Each participant in the SAR443820 treated group will be matched 1:1 using the Mahalanobis distance to a participant in the historical clinical trial database. Matching will be performed with replacement.

To assess the success of the matching procedure, summary statistics of baseline matching variables will be presented and compared between the two treatment groups before and after matching to assess post-match balance.

Post-matching statistical analysis

Once the matching is performed, the comparison between participants who were randomized to SAR443820 and placebo arm generated from the historical trial database will be provided for the following endpoints using the similar analyses models as described for the primary and secondary endpoints in [Section 3.2.2](#) and [Section 3.3.1.2](#).

- Combined assessment of function and survival (CAFS) score at Week 52, Week 76, and Week 104
- Change from baseline in ALSFRS-R total score to Week 52, Week 76, and Week 104
- Time from baseline to the occurrence of either death or permanent assisted ventilation (>22 hour daily for >7 consecutive days) whichever comes first
- Time from baseline to the occurrence of death

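### SAP 3.4.3 still claims superiority over 104 weeks of treatment, and the December 2023 dosing pause is not named as an intercurrent event for the Part B primary or the external control

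*SAP*

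**What the plan says.** SAP 1.1 records the pause: "sites have been instructed on 5th December 2023 to pause the administration of SAR443820 in Part B (open-label extension) immediately". Participants who finish Part A afterwards may roll over for follow-up visits only. A restart depends on a DMC recommendation once Part A data are available. The version history dates SAP version 2 to 08-Jan-2024, before the first database lock, and states: "The first participant was randomized on 28-Apr-2022".

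The efficacy sections read as follows.

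- **SAP 3.1** defines the Part B groups: "Efficacy analyses in Part B will be conducted accumulatively according to the treatment group allocated by randomization in Part A (ie, Placebo/SAR443820 versus SAR443820/SAR443820".
- **SAP 3.2 and 3.3** keep CAFS at Week 52 as the Part B primary. The secondaries include "CAFS at Week 76 and Week 104" and "change from baseline in the ALSFRS-R total score to Week 52, Week 76, and Week 104".
- **SAP 3.4.3** plans a matched comparison with historical controls "to demonstrate the superiority of SAR443820 on slowing down disease progression and prolonging survival over 104 weeks of treatment period".
- **Intercurrent events.** Table 2 names only permanent discontinuation before Week 24. SAP 3.2.2 gives a strategy for stopping IMP under Part A, but for Part B gives only the population and the rank test. SAP 3.3.1.2 applies treatment policy to the Part A and Part B secondaries, as set out in Table 2.

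Protocol 7.1.1 makes discontinuation permanent when interruptions in Part B add up to more than 8 weeks.

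**The concern.** SAP version 2 was approved about five weeks after the pause, yet the analysis sections are worded as if Part B dosing had gone ahead. Three things follow.

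1. SAP 3.4.3 rests on an exposure that the trial can no longer deliver. This comparison sets SAR443820 against untreated historical controls, so the duration of treatment is part of the claim.
2. The event that interrupts dosing for everyone in Part B has no stated strategy for the Part B primary or the external control. For the secondaries, the strategy comes from a table whose event ends at Week 24.
3. Participants still in Part A at the pause get no Part B drug unless dosing resumes. For those allocated to placebo, the label Placebo/SAR443820 describes a treatment they do not receive.

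At stake is how the Part B results may be described. A reader of the report could take Week 76 and Week 104 results as effects of continuous treatment to those visits.

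**Working it through.** **Inputs.** First randomisation 28-Apr-2022 (SAP version history). Pause 5-Dec-2023 (SAP 1.1). All participants past Week 19 on 5-Dec-2023 (Protocol, amendment 05 summary of changes). Part A 24 weeks and Part B 80 weeks (SAP 1.1). Allocation 2:1, 261 planned (SAP 1.1 and 4).

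**Planned durations.** 24 + 80 = 104 weeks of treatment. 4 + 24 + 80 + 2 = 110 weeks in total. Both match the documents.

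**Ceiling at the pause.** 28-Apr-2022 to 5-Dec-2023 is 586 days; 586 / 7 = 83.7 weeks. For a placebo-allocated participant the most SAR443820 exposure is 83.7 − 24 = 59.7 weeks.

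**Latest randomisation date that reaches a visit by the pause** (5-Dec-2023 minus 7 × week):

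| Visit | Randomised by |
|---|---|
| Week 24 | 20-Jun-2023 |
| Week 52 | 6-Dec-2022 |
| Week 76 | 21-Jun-2022 |
| Week 104 | 7-Dec-2021, before the first randomisation |

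The first participant's Week 104 falls on 25-Apr-2024, 142 days (20.3 weeks) after the pause.

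**If dosing resumes.** For the first participant, exposure by Week 104 is 83.7 weeks plus the time from restart to 25-Apr-2024. A restart on 30-Jan-2024 gives 83.7 + 86/7 = 96.0 weeks. Assumed restarts on 1-Mar-2024 and 1-Apr-2024 give 91.6 and 87.1 weeks. A later participant may lose less, but not nothing. Everyone who finishes Part A after the pause rolls over without drug, and the restart waits for Part A data that include the last Week 24 visit.

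**Share of participants affected.** These figures assume no restart and ignore dropout and death. The latest possible randomisation is 5-Dec-2023 − 133 days = 25-Jul-2023, so accrual lasted at most 453 days. The cut-off dates above for Weeks 24, 52 and 76 fall 418, 222 and 54 days after first randomisation. With cumulative accrual (t/453)^k, the share randomised after day t is 1 − (t/453)^k.

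| | k = 0.5 (front-loaded) | k = 1 (uniform) | k = 2 (back-loaded) |
|---|---|---|---|
| No Part B drug (t = 418) | 3.9% | 7.7% | 14.9% |
| Off drug before Week 52 (t = 222) | 30.0% | 51.0% | 76.0% |
| Off drug before Week 76 (t = 54) | 65.5% | 88.1% | 98.6% |

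Under uniform accrual 7.7% is a maximum; it falls if the last randomisation was earlier than 25-Jul-2023. At 2:1, about a third of that group, 7.7% / 3 = 2.6%, is placebo-allocated and never receives SAR443820. On 261 participants that is about 7.

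**Reach of a pre-pause analysis.** With data to the last pre-pause dose + 14 days, taking that dose as 5-Dec-2023, the Week 76 cut-off moves to day 54 + 14 = 68. Under uniform accrual 68/453 = 15.0% could contribute at Week 76. The first participant is then at 600/7 = 85.7 weeks, so nobody contributes at Week 104.

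**Difference between randomised arms.** With x weeks of Part B drug, exposure is 24 + x against x. The planned difference is 24 weeks whether or not the pause shortens x.

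**8-week limit.** 5-Dec-2023 + 56 days = 30-Jan-2024. The documents do not say how this limit applies to a pause that a DMC recommendation may end later.

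**The case against.** The strongest reply is that the randomised Part B comparison was always early start against delayed start. The pause leaves the 24-week exposure difference intact, and off-drug calendar time is common to both arms. A reader might infer that the pause dilutes the randomised effect. The documents do not support that: no dilution can be derived, and late placebo participants who lose their crossover may even preserve separation.

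A reader might also infer that no Part B endpoint has an intercurrent-event strategy. That goes too far, since SAP 3.3.1.2 states treatment policy for the Part B secondaries. The gap there is only the reference to a table that stops at Week 24.

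Nor can it be said that every Part B analysis ignores the pause. The text of SAP 3.2.3 is not visible, and Protocol 9.4.4 sends the CAFS missing-data sensitivity analyses to the SAP. A pause-related analysis there cannot be excluded, but it would not change the visible wording of 3.4.3.

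The labels are partly nominal. SAP 3.1 groups by randomisation, SAP 3.6 uses actual receipt for categorical safety data, and SAP 3.6.1 summarises actual exposure. Relabelling alone would be editorial.

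Finally, no Part B endpoint is in the testing hierarchy (SAP 3.5), and study success rests on Part A (Protocol 9.1). This limits the consequence. None of it answers the 104-week claim or the missing strategy for the Part B primary and the external control.

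**Conclusion.** The point holds in a limited form, as a change that should be made. SAP 3.4.3 attributes to the trial a treatment duration that no participant can have without interruption, even if dosing resumes. That conclusion follows from the dates and from the condition placed on a restart. The visible text names no strategy for the pause for CAFS at Week 52 or for the external control, and only an indirect one for the Part B secondaries.

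Three stronger readings are not supported. First, 84 weeks is not a permanent ceiling: it is the ceiling at the pause and holds only while dosing stays paused. Second, the 8%, 51% and 88% shares are not estimates of what happened. They assume uniform accrual to the latest possible date and no restart; the accrual curves tried give 4 to 15%, 30 to 76% and about 65 to 99%. Third, the pause does not oblige the sponsor to make Weeks 76 and 104 descriptive only. The comparison by randomised arm remains valid, and those endpoints carry no controlled claim. Part A inference is untouched.

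**What to change.** - Keep the Part B comparison by randomised arm under treatment policy. Describe it as early versus delayed start with a pause in dosing, and state that some placebo-allocated participants may never receive SAR443820.
- Name the pause as an intercurrent event, with its strategy, for CAFS at Week 52, the Part B secondaries and the external-control comparison, so that the strategy no longer depends on a table limited to Week 24.
- In SAP 3.4.3, replace the treatment-period wording with follow-up to Week 104. Report actual exposure and time off drug at each visit.
- Add one supplementary analysis of the Part B endpoints and the external control, using data up to the last pre-pause dose + 14 days. SAP 3.2.4 and the on-treatment window in SAP 3.1 provide the model. Tie the cut-off to the pre-pause dose, because a window tied to the final dose would span the pause if dosing resumes. State in advance that few participants contribute at Week 76 and none at Week 104.
- Reconcile the 8-week cumulative limit in Protocol 7.1.1 and 7.1.2 with the possible DMC-led resumption.

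The cost is SAP wording, one extra run and the protocol reconciliation. The price for the sponsor is a narrower Part B claim.

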3.2 PRIMARY ENDPOINT(S) ANALYSIS

The primary endpoint in Part A detailed in this section is change from baseline in the ALSFRS-R total score to Week 24.

The primary endpoint in Part B detailed in this section is CAFS score at Week 52.

3.2.1 Definition of endpoint(s)

Part A

The ALSFRS-R is composed of 12 items across 4 subdomains of bodily function (bulbar, fine motor, gross motor, and breathing), with each item scored on an ordinal scale from 0 (total loss of function) to 4 (no loss of function). The total score of the ALSFRS-R ranges from 0 to 48, with a higher score indicating better function (1). Good reliability between face-to-face and telephone administration of the ALSFRS-R has been demonstrated (2).

Part B

The survival endpoint will be defined as the time to death or permanent assisted ventilation (>22 hours a day for >7 consecutive days), whichever comes first. CAFS is used to compare each study participant's outcome to others in the trial in a series of pairwise comparisons, based on function and survival (3). For each pairwise comparison, a study participant is assigned a score and then the summed scores are ranked for all participants. To calculate a participant's CAFS, each participant is compared individually to all other participants in the trial. The summary score for each participant is the sum of the comparisons (+1, 0, -1) against all other participants. For each pairwise comparison of patients, the participant who fares better earns a point, and the one who fares worse loses a point. In the case of a tie, no points are added or subtracted. If both participants die, the one surviving longer fared better; if only one survives then that participant fared better; and if both participants survive, the one with the smaller decline in ALSFRS-R from baseline fared better. If a participant discontinues early, comparison to each other participant uses time to death if the comparator died; otherwise, the comparison is based on the last ALSFRS-R time-point available for both participants. Once these scores have been calculated for all subjects, they are ranked, from lowest (died first) to highest (best ALSFRS-R outcome among those who survived), yielding the final CAFS score used as the endpoint. The average rank score is then calculated for each treatment group. A higher mean rank score indicates that participants in that treatment group, on average, fared better.

3.2.2 Main analytical approach

Part A

The primary endpoint in Part A will be analyzed with the estimand defined according to the following attributes:

- Endpoint: Change from baseline in the ALSFRS-R total score to Week 24
- Treatment condition: SAR443820 will be compared to placebo
- Analysis population: ITT population
- Intercurrent events (IE):
 - The IMP discontinuation IE will be handled with the treatment policy strategy; The primary endpoint will be assessed based on all assessments irrespective of the IMP discontinuation
- Population-level summary: The primary endpoint will be analyzed using MMRM with change from baseline in ALSFRS-R total score up to Week 24 as response variable, and treatment, visit, randomization strata of the geographic region of the study site, ALS onset region (bulbar or other areas), use of riluzole (yes or no), use of edaravone (yes or no), use of the combination of sodium phenylbutyrate and taurursodiol (yes or no), treatment-by-visit interaction, disease duration (from first symptom onset to the screening visit), baseline ALSFRS-R score, baseline NfL, disease duration-by-visit interaction, baseline NfL-by-visit interaction and baseline ALSFRS-R score-by-visit interaction as covariates. If less than 10 participants in a randomization strata level, then the corresponding factor will not be included as a covariate in the MMRM model.

The least squares mean difference in the ALSFRS-R change from baseline at Week 24 between SAR443820 vs placebo, together with the p-value and the 95% CI for the difference, will be estimated from the MMRM model using weights for each stratum equal to the overall proportion of participants in each stratum (ie, “population weight”) by inclusion of the OBSMARGINS option in the LSMEANS statement. Plots of least squares means (\pm standard error) over time will be provided.

This model will be implemented using the SAS MIXED procedure with an unstructured covariance matrix to model the within-participant errors. Parameters will be estimated using the restricted maximum likelihood method. The denominator degrees of freedom will be estimated using the Kenward-Roger approximation. This model will provide baseline adjusted least-squares means estimates at Week 24 for SAR443820 and placebo, together with their corresponding standard errors and CIs. If this model fails to converge, the following variance-covariance structures will be tested in this order:

- Heterogeneous Toeplitz
- Heterogeneous AR(1)
- Heterogeneous CS
- Toeplitz

- AR(1)
- CS.

[figure not shown]
The first (co)variance structure yielding convergence will be used as the primary analysis. When a variance-covariance structure other than unstructured is used, the denominator degree of freedom will be estimated using the between within method (DDFM=BW in SAS PROC MIXED) (4).

We assume a priori that change from baseline in the ALSFRS-R total score to Week 24 are normally distributed. Given the large sample size, the impact of violation of normality should not be great. In order to assess the impact of deviation from the normality assumption, a sensitivity analysis using rank analysis of covariance (ANCOVA) with the same covariates as for the MMRM analysis except visit and related interaction terms, will be performed to test the significance of the treatment effect.

Part B

CAFS score at Week 52 will be analyzed in the mITT population using the Wilcoxon-Mann-Whitney test to compare mean scores between the treatment groups at Week 52.

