3.3.1.2 Main analytical approach

Treatment policy will be used for the analyses of all secondary endpoints in Part A and Part B as stated in [Table 2](#).

CAFS

CAFS at Week 24, Week 76 and Week 104 will be analyzed in the same manner as that used to analyze the primary endpoint in Part B in [Section 3.2.2](#).

Continuous Endpoints

Continuous endpoints include:

Part A

- change from baseline in SVC to Week 24
- change from baseline in muscle strength to Week 24
 - change from baseline in megascore to Week 24
 - change from baseline in grip strength to Week 24
- change from baseline in ALSAQ-5 to Week 24
- change from baseline in serum NfL to Week 24

Part B

- change from baseline in the ALSFRS-R total score to Week 52, Week 76, and Week 104
- change from baseline in SVC to Week 52, Week 76, and Week 104
- change from baseline in ALSAQ-5 to Week 52, Week 76, and Week 104
- change from baseline in serum NfL to Week 52

These continuous endpoints will be analyzed using the same manner as that used to analyze the primary endpoint in Part A in [Section 3.2.2](#), except that baseline ALSFRS-R score will be replaced by the baseline value of the corresponding endpoint. Plots of least squares means (\pm standard error) over time will be provided. Plots of mean (\pm SD) and/or mean change (\pm SD) and/or median over time will also be provided. For NfL data, log transformation will be applied in

the MMRM model. The treatment difference will then be back-transformed to the original scale. The back-transformed LS means stand for geometric mean ratios compared to baseline, and the back-transformed LS means difference stands for ratio of the geometric mean ratios compared to baseline between SAR443820 and placebo. In order to assess the impact of deviation from the normality assumption, a sensitivity analysis using rank analysis of covariance (ANCOVA) with the same covariates as for the MMRM analysis except visit and related interaction terms, will be performed to provide the p-value for the comparison between the treatment groups.

Time-to-event endpoints

Time-to-event endpoints in Part B include:

[figure not shown]
- time from baseline to occurrence of either death or permanent assisted ventilation (>22 hours daily for >7 consecutive days), whichever comes first
- time from baseline to the occurrence of death

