4 SAMPLE SIZE DETERMINATION

The proposed sample size ($n = 261$) provides an approximately 80% power to detect a 30% reduction in SAR443820 compared with placebo in the change of ALSFRS-R from baseline at Week 24, assuming a change of █ points from baseline in ALSFRS-R in the placebo arm with a standard deviation of █ points, and a 20% drop-out rate. Sample size is estimated via simulation with a 2-sided 5% significance level.

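### If the unstructured MMRM fails to converge, the fallback structures in SAP 3.2.2 run with model-based standard errors, which can misstate the type I error of the Week 24 primary test

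*SAP*

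**What the plan says.** SAP 3.2.2 sets the main model: "This model will be implemented using the SAS MIXED procedure with an unstructured covariance matrix to model the within-participant errors", estimated by REML with Kenward-Roger degrees of freedom. Protocol 9.4.2 gives the same model and no fallback.

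On non-convergence, SAP 3.2.2 lists six structures in order: heterogeneous Toeplitz, heterogeneous AR(1), heterogeneous CS, Toeplitz, AR(1), CS. Then "The first (co)variance structure yielding convergence will be used as the primary analysis". For any of these, "the denominator degree of freedom will be estimated using the between within method (DDFM=BW in SAS PROC MIXED").

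Nothing is said about the standard error under a fallback. Robust variance is specified in the SAP for the Cox model (3.3.1.2), but for no MMRM.

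SAP 3.3.1.2 carries the rule to the continuous secondary endpoints of Parts A and B: "These continuous endpoints will be analyzed using the same manner as that used to analyze the primary endpoint" in Part A. SAP 3.5 limits the hierarchical 5% procedure to the Part A primary endpoint and selected Part A secondary endpoints.

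**The concern.** An unstructured covariance imposes no pattern, so its model-based standard errors do not depend on having guessed one. Each fallback does impose a pattern. If that pattern is wrong, the standard error of the last-visit contrast is wrong, and changing the degrees of freedom does not repair it.

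There is reason to doubt the patterns here. People with ALS decline at different rates: the entry criterion in Protocol 5.1 sets a minimum prestudy slope and no maximum, and SAP 3.3.1.1 contrasts fast and slow progressors. Varying slopes make both the variance and the correlation between visits change with time. The three heterogeneous structures give each visit its own variance, so they do allow variance to grow; their misfit is in the correlation pattern. The three homogeneous structures miss both.

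At stake is whether the Week 24 test keeps its 5% level if a fallback becomes the primary analysis.

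**Working it through.** **Inputs from the documents.** Level: "Sample size is estimated via simulation with a 2-sided 5% significance level". Allocation: "randomized in a ratio of 2:1 to receive 20 mg BID SAR443820 (n=174) or placebo BID (n=87"). Loss: "and a 20% drop-out rate". Post-baseline ALSFRS-R visits: Weeks 4, 8, 12, 16, 20 and 24 in Part A (the extracted schedule row is misaligned; Week 24 is counted because the primary endpoint needs it), then Weeks 28, 36, 44, 52, 64, 76, 88 and 104 in Part B.

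**The plan's own figure.** SAP 4 says that N = 261 "provides an approximately 80% power to detect a 30% reduction in SAR443820 compared with placebo in the change of ALSFRS-R". The placebo change and SD are redacted and N came from simulation, so it cannot be recomputed. Working back from 174 × 0.8 = 139.2 and 87 × 0.8 = 69.6 evaluable participants:

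δ/SD = (1.96 + 0.8416) × √(1/139.2 + 1/69.6) = 2.8016 × 0.1468 = 0.411,

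so the placebo change/SD is 0.411/0.30 = 1.37. This says nothing about the covariance between visits, which must be assumed.

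**Assumptions (not in the documents).** Random slopes with SD 0.5 to 1.0 points/month; residual SD 1.5, with 1 to 2 as the range; intercept SD 0.5 to 1.0; dropout unrelated to outcome, 20% by Week 24. Model covariates are omitted.

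**Size of the models.** With T visits the unstructured covariance has T(T+1)/2 parameters: 21 for the 6-visit primary model and 14 × 15/2 = 105 for ALSFRS-R to Week 104.

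**Formula.** For each fallback, find the covariance to which the fit converges under the assumed truth, then compare the model-based variance of the last-visit treatment contrast with its true variance:

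type I error = 2Φ(−1.96 × √(model variance / true variance)).

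**A case that can be checked by hand.** Take CS, no dropout, intercept SD 0.8, slope SD 0.8, residual SD 1.5, with 4 weeks = 0.92 months. The true variance at visit k is 0.64 + 0.64 × (0.92k)² + 2.25 ≈ 2.89 + 0.542k². At Week 24 (k = 6) this is 22.4. CS fits one common variance, the average over visits: 2.89 + 0.542 × 91/6 = 11.1. The ratio is 0.496, its root is 0.704, and 2Φ(−1.38) = 16.8%.

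**All six structures at Week 24, 20% loss, residual SD 1 to 2, with or without added Brownian drift:**

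| Structure | Type I error (nominal 5%) |
|---|---|
| Heterogeneous Toeplitz | 6.4%–10.5% |
| Heterogeneous AR(1) | 6.3%–10.0% |
| Heterogeneous CS | 5.8%–6.3% |
| Toeplitz | 11.4%–16.1% |
| AR(1) | 11.4%–18.6% |
| CS | 11.9%–21.5% |

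A separate calculation with residual SD fixed at 1.5 gives 7.4%–9.8%, 7.1%–9.4% and 6.3%–6.6% for the three heterogeneous structures and 16%–21% for CS. The small difference for heterogeneous CS reflects sensitivity to the intercept variance assumed.

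**Other true covariances at Week 24.** If the chosen structure is correct, the error is 5.0%. With flat variance and CS or AR(1) correlation, all six lie between 4.6% and 5.6%. With growing variance and a heterogeneous Toeplitz or CS truth, the heterogeneous structures give 4.7%–5.0% and the homogeneous ones 15.9%–17.4%. With variance that shrinks over time, the homogeneous structures give 0%–0.1%.

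**Simulation at 174 v 87, REML, t on 259 df.** At Week 24 (20% loss, 1000 runs, Monte Carlo SE √(0.05 × 0.95/1000) = 0.7 points):

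| Intercept / slope / residual SD | Structure | Model-based | Sandwich |
|---|---|---|---|
| 0.8 / 0.8 / 1.5 | Het. Toeplitz | 8.5% | 5.4% |
| | Het. CS | 5.9% | 5.3% |
| | CS | 17.8% | 5.7% |
| 1.0 / 0.5 / 2.0 | Het. Toeplitz | 6.2% | 5.2% |
| | Het. CS | 6.0% | 5.0% |
| | CS | 11.0% | 5.2% |

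**Week 104, 14 visits, 30%–50% loss assumed.** Calculated error is 13.1%–16.1% for heterogeneous Toeplitz, 12.4%–16.4% for heterogeneous AR(1) and 5.8%–7.0% for heterogeneous CS. In 400 simulated runs at 50% loss (1.0 / 0.5 / 2.0), heterogeneous AR(1) gave 10.5% model-based and 5.2% with the sandwich. Gaps between visits run from 4 to 16 weeks, whereas Toeplitz and AR(1) count lag by visit number, which is a further source of misfit.

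**The case against.** The strongest reply is that the rule may never operate, and that nothing in the documents shows the direction of any error. Much of this stands.

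- A reader might infer that the fallback p-value is anti-conservative. The documents do not support that: they give no covariance, and the check above yields nominal and conservative cases as well. The by-visit terms for baseline score, NfL and disease duration may also absorb some slope variation, which the calculations ignore.
- A reader might infer that none of the fallbacks can represent spreading trajectories. The first three allow it in the variances. The larger errors need all three to fail first.
- A reader might infer that the Part A secondary endpoints are exposed too. SVC, muscle strength, ALSAQ-5 and NfL appear to have three post-baseline visits in Part A (Weeks 8, 16 and 24), hence 3 × 4/2 = 6 covariance parameters, so a fallback is very unlikely. CAFS is a Wilcoxon test.
- A reader might infer that Part B error control is threatened. Part B is outside the hierarchy of SAP 3.5, and its primary endpoint is CAFS. The 14 visits apply to ALSFRS-R only; SVC and ALSAQ-5 have 11.
- Model-based standard errors are inferred from silence and the software default. The reference cited for the between-within method is not available here.

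What does not stand is that trying heterogeneous Toeplitz first makes the rule safe: under random slopes that structure gives 6.4%–10.5%.

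**Conclusion.** The gap is real but conditional. Followed literally, SAP 3.2.2 makes a possibly misspecified covariance the basis of the primary p-value with no protection for its standard error. Under the assumed random-slope covariance (slope SD 0.5 to 1.0 points/month, residual SD about 1.5, 20% loss), Week 24 type I error is about 6% to 10% for the heterogeneous structures, mildest for heterogeneous CS at about 6% to 7%, and about 11% to 21% for the homogeneous ones.

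The confirmatory consequence is confined to the Part A Week 24 primary test, and arises only if the unstructured model fails. The ALSFRS-R models to Week 104, with 105 covariance parameters and attrition, are a plausible place for a fallback, but there the cost is to descriptive inference. The probability of non-convergence cannot be computed from the documents for either model. The point should be settled before any fallback result is seen; it is no reason to doubt the primary analysis if the unstructured model converges.

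**What to change.** Add to SAP 3.2.2:

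1. Before any fallback, attempt to make the unstructured model converge, using starting values and an alternative parameterisation.
2. If another structure is still needed, fit the full-population MMRM with the EMPIRICAL (sandwich) option, keeping DDFM=BW.

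Carry both through 3.3.1.2 to the Part B continuous endpoints. For the subgroup models in 3.2.5, use a small-sample-corrected sandwich or leave the rule out. A category at the 10% threshold has about 26 people; in simulations on complete data with three by-visit covariates, the uncorrected sandwich gave 8.8% at 17 v 9 and 6.8% at 35 v 17, against about 5% at 174 v 87.

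The cost is a short SAP addition and one SAS option, unused if the unstructured model converges. There are three downsides. The sandwich standard error is slightly more variable. It is anti-conservative in small samples. It also does not remove bias in the point estimate when the covariance is wrong and data are missing at random, as the SAP assumes, rather than completely at random; this is why step 1 comes first.
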